6.5.8.3 Adverse Events and Unanticipated Adverse Device Effects

An AE is defined as any untoward medical occurrence, unintended disease or injury, or untoward clinical signs (including abnormal laboratory finds) in subjects, users, or other persons, whether or not related to the investigational medical device.

The following AEs are the key safety events surveilled during the study in order to assess conformity to the target values of "Incidence of Adverse Events".

- Loss of > 2 lines (10 letters) BSCVA
- BSCVA worse than 20/40
- BSCVA worse than 20/25 if 20/20 or better preoperatively
- Haze \geq trace with loss of BSCVA > 2 lines (10 letters)
- Increased manifest refractive astigmatism > 2.0 D
- Corneal epithelial defect involving the keratectomy at one month or later
- Melting of the flap
- Miscreated flap (lost, incomplete, too thin)
- Diffuse lamellar keratitis (Grade 3 or above)
- Corneal infiltrate or ulcer

- Any persistent corneal epithelial defect at one month or later
- Epithelium in the interface with loss of 2 lines (10 letters) or more BSCVA
- IOP with increase of > 10 mmHg above baseline on two consecutive examinations or an IOP greater than 30 mmHg on two consecutive examinations
- Haze beyond 6 months with loss of 2 lines or greater (≥ 10 letters ETDRS) of BSCVA
- Decrease in BSCVA of greater than or equal to 2 lines (≥ 10 letters ETDRS) not due to irregular astigmatism as shown by rigid contact lens refraction at 3 months or later
- Retinal detachment
- Corneal edema at 1 month or later
- Retinal vascular accidents
- Ocular penetration
- Other ocular event

All UADEs are considered to be rare, unanticipated events and have a serious effect on health or safety or represent any life-threatening problem or death caused by the device, if the event has not previously been identified in the investigational plan. A UADE may include, but is not limited to, the following events:

- Device-related death
- Enucleation of treated eye
- Corneal transplant of treated eye

A summary (counts and percentages) of AEs/UADEs will be presented by incidence of AEs for operative visit, each postoperative study visit, and overall (a Total column) using all treated eyes. At a study visit subjects' eyes will be counted only once if they experience multiple AEs/UADEs of the same type and similarly will be counted only once in Total column if they have AEs/UADEs of the same type at multiple study visits.

The number and percentage of eyes with at least one serious, device-related adverse event during the study will be presented along with a two-sided 95% exact CI around the proportion.

All AEs/UADEs will be presented in a data listing by subject. The AEs/UADEs leading to study discontinuation will be listed separately.

6.5.8.4 Complications/Potential Adverse Events

Complications/Possible AEs are known to potentially occur in association with laser refractive surgery and include the safety events listed below:

- Allergic conjunctivitis
- Blepharitis
- Conjunctivitis
- Corneal abrasion
- Corneal edema between 1 week to less than 1 month after procedure
- Corneal flap lifting between 1 day to 1 month post-surgery for wrinkled flap
- Corneal haze
- Corneal scar
- Debris in the interface
- Diffuse lamellar keratitis (grade 2 or less)
- Double/ghost images in operative eye
- Dry eye
- Enhancement not done due to flap fibrosis
- Epithelium at the flap edge
- Epithelium in the interface
- Flap is not of the size and shape as initially intended or resultant flap is misaligned
- Foreign body sensation at 1 month or later
- Iritis
- Loose epithelium
- Meibomian gland dysfunction

- Mucus under edge of flap
- Pain at 1 month or later
- Peripheral corneal epithelial defect at 1 month or later
- Possible allergic reaction to plugs or eye drops
- Postoperative flap complications
- Punctal plug inserted
- Punctal plug replaced
- Rough epithelium
- Superficial punctate keratopathy (SPK)
- Steroid induced IOP increase
- Subconjunctival hemorrhage
- Transient light-sensitivity syndrome (TLSS)
- Trace microstriae
- Trace corneal haze
- Vitreous floaters
- Other

Complications/potential AEs will be summarized in a similar manner as AEs/UADEs for operative visit, each postoperative visit, and overall (a Total column) using all treated eyes.

All complications/potential AEs also will be presented in a data listing by subject. The complications/potential AEs leading to study discontinuation will be listed separately.

6.5.8.5 Endothelial Cell Density (ECD) Sub-Study

Preoperative and postoperative (Month 6) corneal ECDs will be measured by specular microscopy for both eyes (regardless whether one or both eyes are treated) of up to approximately 90 subject eyes undergoing LASIK surgery at two or more clinical sites. To determine ECD, sites will submit all preoperative and Month 6 postoperative images to the central reading center for image analysis.

A table will be provided for change from baseline in ECD at Month 6 and categorical percent loss in ECD including > 0%, > -10% to <= 0%, > -20% to <= -10%, > -30% to <= -20%, > -40% to <= -30%, > - 50% to <= -40%, and <= -50%

A data listing by subject and by study visit will be provided for the date ECD was performed and the mean ECD result will be provided by the central reading center for up to three analyzable images taken at a study visit.

6.5.8.6 Contrast Sensitivity Testing Sub-Study

At least approximately 50 subjects will have their eyes enrolled in a sub-study to have monocular and binocular contrast sensitivity testing performed, testing which will be conducted at three or more clinical sites. The subjects in this sub-study may be, although are not required to be, any of the subjects in the specular microscopy testing sub-study. Testing will be conducted using a commercially available contrast sensitivity instrument of the same make and model at each of the two or more clinical sites. Each instrument will be calibrated according to the manufacturer and capable of conducting binocular mesopic (approximately 3.0 ± 2.0 cd/m²) contrast sensitivity measurements with and without glare at spatial frequencies of 1.5, 3, 6, and 12 cpd. The contrast sensitivity measurements will be made at the optimal distance recommended by the instrument manufacturer.

Subjects will practice the contrast sensitivity test once at each of two randomly selected spatial frequencies under mesopic conditions without glare before beginning tests for recorded data. Contrast sensitivity will be assessed twice for each subject at each test condition at the Preoperative Visit and postoperatively at the Month 6 Visit. Mean contrast sensitivity of the two assessments at each visit and change from baseline results will be summarized in a table using all treated subjects.

A data listing by subject of contrast sensitivity results will be provided.

6.5.8.7 Schirmer's Test

Appropriate commercial paper strips for conducting a Schirmer's test without anesthesia are placed in the inferior fornix extending outward of both eyes and subjects are instructed to close their eyes for 5 minutes. The test strips are then removed, and the migration distance of strip wetness is measured in mm. No topical anesthetic may be used.

Schirmer's test is conducted in each eye at the Preoperative Visit and postoperatively at the Month 6 Visit. Tear fluid secretion from the Schirmer's test will not be summarized in a table.

A data listing by subject of Schirmer's test results will be provided.

6.5.8.8 Intraocular Pressure (IOP)

The measurement of eye pressure is part of a routine eye examination in which the IOP is determined. Goldmann applanation tonometry is the most accurate method and as such is the preferred method for study subjects. However, if an alternative method (e.g., Tonopen) is required at any site, it will be allowed. In any event, the same testing method is to be employed for all study visits for each subject to facilitate reliable comparisons from visit to visit. If cycloplegic refraction is measured the same day as IOP, the IOP should be measured following the refraction to avoid disturbing the corneal surface.

Intraocular pressure is measured at the Preoperative Visit and postoperatively at the Month 1, Month 3, Month 6, and Month 9 Visits. The IOP measurements and changes from baseline for each eye will not be summarized in a table.

A data listing by subject of IOP results will be presented.

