All subjects, regardless of the time of individually achieving refractive stability, will be followed up until the last study visit (Visit 8) which is Month 9 post-operatively. Upon completion of Visit 8, all subjects will be exited from the study.

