8.1 Adverse Events

An adverse event (AE) as defined in ISO standard 14155 is "any untoward medical occurrence, unintended disease or injury, or untoward clinical signs (including abnormal laboratory findings) in subjects, users, or other persons, whether or not related to the investigational medical device."

The following AEs are the key safety events surveilled during the study. Each occurrence of these AEs must be reported to the Sponsor by recording in the AE CRF within 48 hours, and in addition, must be reported to the IRB per IRB policy (See Table 2).

- Loss of > 2 lines (10 letters) BSCVA
- BSCVA worse than 20/40
- BSCVA worse than 20/25 if 20/20 or better preoperatively
- Haze \geq trace with loss of BSCVA > 2 lines (10 letters)
- Increased manifest refractive astigmatism > 2.0 D
- Corneal epithelial defect involving the keratectomy at one month or later
- Melting of the flap
- Miscreated flap (lost, incomplete, too thin)
- Diffuse lamellar keratitis (Grade 3 or above) ⁴²
- Corneal infiltrate or ulcer
- Any persistent corneal epithelial defect at one month or later
- Epithelium in the interface with loss of 2 lines (10 letters) or more best spectacle corrected visual acuity (BSCVA)
- Intraocular Pressure (IOP) with increase of >10 mmHg above baseline on two consecutive examinations or an IOP greater than 30 mmHg on two consecutive examinations
- Haze beyond 6 months with loss of 2 lines or greater (≥ 10 letters ETDRS) of BSCVA
- Decrease in BSCVA of greater than or equal to 2 lines (≥ 10 letters ETDRS) not due to irregular astigmatism as shown by rigid contact lens refraction at 3 months or later
- Retinal detachment
- Corneal Edema at 1 month or later
- Retinal vascular accidents
- Any other vision-threatening event
- Ocular penetration

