8.4 Complications / Possible Adverse Events

Complications / possible adverse events are known to potentially occur in association with laser refractive surgery and include the safety events listed below. Each occurrence of these safety events will be recorded in the postoperative CRFs only and will not be reported to the Sponsor or the IRB (See Table 2, "Safety Event Reporting"):

- Allergic conjunctivitis
- Blepharitis
- Conjunctivitis
- Corneal abrasion
- Corneal edema between 1 week to less than 1 month after procedure
- Corneal flap lifting between 1 day to 1-month post-surgery for wrinkled flap
- Corneal haze

- Corneal scar
- Debris in the interface
- Diffuse lamellar keratitis (grade 2 or less) ⁴²
- Double/ghost images in operative eye
- Dry eye
- Enhancement not done due to flap fibrosis
- Epithelium at the flap edge
- Epithelium in the interface
- Flap is not of the size and shape as initially intended or resultant flap is misaligned
- Foreign body sensation at 1 month or later
- Iritis
- Loose epithelium
- Meibomian gland dysfunction
- Mucus under edge of flap
- Pain at 1 month or later
- Peripheral corneal epithelial defect at one (1) month or later
- Possible allergic reaction to plugs or eye drops
- Postoperative flap complications
- Punctal plug inserted
- Punctal plug replaced
- Rough epithelium
- Superficial punctuate keratopathy (SPK)
- Steroid induced IOP increase
- Subconjunctival hemorrhage
- Transient light-sensitivity syndrome (TLSS)
- Trace microstriae
- Trace corneal haze
- Vitreous floaters

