9.6.3.3 Additional Safety Analyses

The following additional safety summaries will be provided with descriptive statistics by visit.

- Eyes with BSCVA worse than 20/40 among eyes that had a BSCVA of 20/20 or better before surgery at each study visit, stratified by preoperative MRSE, and stratified by preoperative cylinder
- Loss of BSCVA of 1, $2, \ge 2$, and > 2 lines
- Percentage of eyes that have an increase of manifest refractive astigmatism > 2.00 D of manifest cylinder compared to the preoperative refraction
- Eyes treated for sphere only that have a magnitude of postoperative manifest refractive astigmatism that increases from baseline cylinder by > 2.00 D at the postoperative interval at which stability has been established, and stratified by preoperative MRSE

- Incidence of adverse events by event type
- Frequency of miscreated flaps
- Incidence of complications
- Endothelial cell density changes
- Contrast sensitivity changes, mesopic conditions
- Schirmer's Test results, Preoperative Visit and Month 6 Visit
- Intraocular Pressure
- Subject symptoms and results for prespecified question domains (from PROWL questionnaire)

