- 95% CIs for percentage of eyes with the loss of BSCVA of 1, 2, ≥ 2, and > 2 lines compared to preoperative BSCVA and for percentage of eyes that have an increase of manifest refractive astigmatism > 2.00 D compared to the preoperative refraction will be presented.
- The percentage of eyes with at least one serious, device-related adverse event during the study along with 95% CI will be presented.
- Contrast sensitivity results will not be reported as graphs as stated in the protocol but will be summarized in a table.
- Schirmer's test results will not be summarized in a table.
- Intraocular pressure results will not be summarized in a table.
- Changes to questionnaire data analysis.
 - In the protocol, Table 3 has questions for topics Visual Functions and Near Vision overlapped. In SAP, topic Vision Functions is removed, and questions are combined under Near Vision.
 - Topic Expectation of LASIK Surgery in protocol Table 4 is considered a subjective measure that may have potential threats to the validity. The results will not be summarized but only provided in questionnaire listing.
 - Questions not covered in protocol Table 3 and Table 4 are not the main interest to the study. The results will not be summarized but only provided in questionnaire listing.

Documentation of revision to the SAP will commence after approval of Version 1.0.

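### The SAP drops the protocol's IOP and Schirmer's summaries without a reason, so a single-visit pressure rise that is neither rechecked nor entered under another event row would appear only in a listing

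*SAP*

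**What the plan says.** Protocol 9.6.3.3 lists safety summaries to be given as descriptive statistics by visit. IOP is one item; another is "Schirmer's Test results, Preoperative Visit and Month 6 Visit". SAP section 4 says that the SAP's methods supersede the protocol's. The SAP leaves both items out of its safety list in 6.5.8. On IOP, 6.5.8.8 says "The IOP measurements and changes from baseline for each eye will not be summarized in a table". On tear production, 6.5.8.7 says "Tear fluid secretion from the Schirmer's test will not be summarized in a table". A by-subject listing remains for each.

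SAP 6.6 declares both removals, for example "Intraocular pressure results will not be summarized in a table", and gives no reason for either. It does give reasons for several other changes: the imputation method, two redundant stability items and some questionnaire topics.

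The listed IOP adverse event, in protocol 8.1 and again in SAP 6.5.8.3, is an IOP "with increase of >10 mmHg above baseline on two consecutive examinations or an IOP greater than 30 mmHg on two consecutive examinations". Protocol 8.4 and SAP 6.5.8.4 also carry the complication "Steroid induced IOP increase", with no threshold and no required number of readings. The SAP adds a catch-all row to each of the two event lists. It tabulates adverse events and complications by visit and overall.

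Postoperative tonometry is scheduled at Months 1, 3, 6 and 9 (protocol Appendix A; SAP 6.5.8.8). On the end of follow-up, protocol 7.1.3.5 says "Upon completion of Visit 8, all subjects will be exited from the study".

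**The concern.** The two-examination rule and the visit schedule work against each other. With readings this far apart, two consecutive raised scheduled readings describe a rise that lasted for weeks or months. The protocol's by-visit IOP summary was the planned output that did not depend on that rule or on how a site classified an event. Once it is removed, the tables show IOP only through event categories: one with a strict definition, and others with no numerical definition.

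What is at stake is the completeness of the safety report. Collecting safety data is part of the primary objective (protocol section 4; SAP section 5), and SAP 6.5.8.3 uses the listed events to judge conformity with target values for adverse event incidence. A reader of the tables could not tell how many eyes had a raised reading at one examination.

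Schirmer's is the same kind of deletion. Dry eye is a risk named in protocol 3.3, and Schirmer's is the schedule's only direct measurement of tear production, yet the tables would give no estimate of its value before surgery or at Month 6.

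**Working it through.** The plan states no figure to reproduce here. The check uses the visit windows and the event definition.

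**Inputs.** Windows in weeks after surgery (protocol 7.1): Month 1, 3-5; Month 3, 10-14; Month 6, 21-26; Month 9, 35-43. No tonometry is scheduled at Day 1 or Week 1. The event definition is in protocol 8.1.

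**Formula.** Shortest gap = opening of the later window minus closing of the earlier one. Longest gap = closing of the later window minus opening of the earlier one.

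| Pair of readings | Shortest (weeks) | Longest (weeks) |
|---|---|---|
| Month 1 to Month 3 | 10 - 5 = 5 | 14 - 3 = 11 |
| Month 3 to Month 6 | 21 - 14 = 7 | 26 - 10 = 16 |
| Month 6 to Month 9 | 35 - 26 = 9 | 43 - 21 = 22 |

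**What this means for the listed event, on in-window scheduled readings alone:**

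1. A rise must last at least 5 weeks to be present at two consecutive postoperative readings.
2. A rise that starts after the Month 1 reading and ends before the Month 6 reading meets at most one reading. Those two readings are 21 - 5 = 16 to 26 - 3 = 23 weeks apart.
3. The same holds between the Month 3 and Month 9 readings, which are 35 - 14 = 21 to 43 - 10 = 33 weeks apart.
4. A rise that starts after the Month 6 reading can meet only the Month 9 reading, and no scheduled reading follows that could confirm it.
5. A rise that has resolved before week 3 meets no scheduled reading. Restoring a table would not recover it unless it was measured at an unscheduled visit.

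**Where a single raised reading can be reported under the SAP:**

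| Output | Threshold | Depends on |
|---|---|---|
| Two-examination adverse event | Yes | A second consecutive raised examination |
| Steroid-induced rise (complication) | None | Investigator's causal attribution |
| Catch-all adverse event or complication row | None | Investigator's decision to enter it; the row pools unrelated events |
| By-subject listing | None | Nothing; every value is shown, none is summarised |

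Only the listing is certain to show a single raised reading. No planned output gives the rate of such readings against a threshold.

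**The case against.** The strongest reply is that several routes into a table remain open.

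- The two-examination rule defines one listed event. The general definition in protocol 8.1 covers any untoward clinical sign, and the SAP has catch-all rows.
- A rise attributed to steroids can be tabulated as a complication after one reading.
- The rule refers to examinations, which need not be scheduled visits. Protocol 7.1.4 allows additional visits for subjects' safety, so a high reading may well be repeated before the next scheduled visit.
- The removals are declared, the listings show every value, and protocol 9.6.1 promises analysis datasets, with programs in the submission.
- Dry eye is still estimated through the dry eye complication and the PROWL eye dryness domain.

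All of this stands, and it rules out stronger readings. A reader might infer that transient or late rises can appear in no table; the routes above show that they can. A reader might infer that the event is seldom attainable or that its reported incidence is biased low. The documents give no frequency of single rises or of rechecks, and a definition that asks for a sustained rise is not biased because it leaves out an unsustained one. Nor are all of the roughly 334 eyes affected: the gap concerns only an eye with one raised reading that was neither rechecked nor entered elsewhere.

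The reply does not supply the missing summary. The remaining routes depend on investigator judgement, and no passage requires a second IOP reading. Follow-up beyond exit (protocol 5.3.3) is tied to an adverse event, which a single reading is not under the listed definition. The complication and questionnaire outputs do not measure tear production.

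**Conclusion.** The point holds in a limited form. The SAP removes two descriptive safety summaries that the protocol planned, without giving a reason. For IOP, this leaves a reporting gap for a rise seen at one visit or first seen at Month 9, provided that it is not rechecked at an unscheduled visit and not entered as steroid-induced or under a catch-all row. Such a rise would appear only in a listing.

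The gaps of 5 to 22 weeks assume in-window scheduled visits with no reading in between. How many eyes would fall into the gap cannot be derived from the documents.

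Severity is minor. This is a declared but unexplained reduction in safety reporting, and a reader should not take it for a hidden contradiction between the two documents. No primary endpoint, hypothesis or success criterion changes.

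**What to change.** **Restore what the protocol planned.** In SAP 6.5.8.8, summarise IOP by visit for all treated eyes. In 6.5.8.7, summarise Schirmer's at the Preoperative and Month 6 visits. Add both to the list in 6.5.8 and delete the two removal bullets in 6.6.

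**Add a small new item, labelled as new because protocol 9.6.3.3 does not promise it.** Show change from baseline. For IOP, also show by visit and overall the number and percentage of eyes with a rise above 10 mmHg or a value above 30 mmHg on any single examination, beside the number meeting the two-examination event. State the denominator as eyes with a reading. Include unscheduled visits in the counts, since protocol 7.1.4 records out-of-window visits there.

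**Add a footnote** that single readings include measurement noise. Leave the adverse event definition and clinical management unchanged.

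The cost is two descriptive tables from data already collected. The drawback is that isolated high readings, some of them noise, become visible and need that footnote.

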6.5.8.9 PROWL Questionnaire

The PROWL-PRQ and PROWL-POQ will be administered to all subjects. Subjects will complete PROWL questionnaires at the Preoperative Visit and postoperatively at the Month 3, Month 6, and Month 9 Visits.

Results obtained both pre- and post-LASIK surgery will be assessed for selected topic domains of near vision, far vision, eye dryness, subject symptoms, driving, and vision clarity. **Table 3** describes the specific pre-operative PROWL-PRQ and post-operative PROWL-POQ questions to be analyzed for each of these topic domains. Normalization of individual or domain scores, if required, will be done as described in the Hays RD paper [5] or relevant primary references annotated in the PROWL questionnaire reference. Domain score for each subject will be provided as the average score of all questions within a domain after normalization as shown in **Table 3a**.

Normalized results for other PROWL-PRQ and/or PROWL-POQ categories of vision satisfaction, vision clarity, and satisfaction with LASIK surgery will be analyzed. **Table 4** describes the specific PROWL-PRQ and PROWL-POQ questions to be summarized for each of these categories with normalization score details provided in **Table 4a**.

Domains presented in Tables 3 and 4 will be summarized by study visit using continuous descriptive statistics including change from baseline.

Topics - Pre and Post LASIK surgery	PROWL-PRQ questions	PROWL-POQ questions
Far Vision	16-18 and 28-29	10-12 and 22-23
Near Vision	19 and 24-27	13 and 18-21
Eye Dryness	65-72	62-69
Subject Symptoms	45-64	42-61
Driving	12-18	6-12
Vision Clarity	34-36a	28-30a

Table 3. PROWL Topic Domain Categories and Domain Questions to be Analyzed

Table 4a	. Normalized	Scores for	PROWL	Questions	in Table 3
----------	--------------	------------	-------	-----------	-------------------

Topics - Pre and Post LASIK surgery	PROWL-PRQ questions	PROWL-POQ questions	Normalized Score
Far Vision	16-17	10-11	No difficulty at all =100 A little difficulty = 75 Moderate difficulty = 50 A lot of difficulty = 25 Never drive at night because of vision, or Never drive in these condition because of vision = 0 Never drive at night for other reasons or Never drive in these condition for other reasons = N/A
		•	No difficulty at all =100 A little difficulty = 200/3 Moderate difficulty = 100/3 A lot of difficulty = 0 all questions within the domain)/(total
number of questions answered) Note: Questions with answers as N/A will be treated as not answer excluded from the mean domain score calculation.			ore calculation.
Near Vision	19	13	No difficulty at all =100

			A little difficulty = $200/3$
			Moderate difficulty = $100/3$
			A lot of difficulty = 0
			No difficulty at all =100
			A little difficulty $= 75$
			Moderate difficulty $= 50$
			A lot of difficulty = 25
		10.00	Never try to do these activities
	24-26	18-20	because of vision or Never try to do
			this because of vision $= 0$
			Never do these activities for other
			reasons or Never do this for other
			reason = N/A
			Yes, many = 0
	27	21	
	21	21	Yes, one or a few $= 50$
	D i		No = 100
			all questions within the domain)/(total
	number of question	,	
	-		A will be treated as not answered and
	excluded from the	e calculation.	
			None of the time $= 4$
	65-72		Some of the time $= 3$
		62-69	Half of the time $= 2$
Eye Dryness			Most of the Time $= 1$
			All of the Time $= 0$
	Domain score =	[(sum of scores of	of all questions within the domain) x
	100]/[(total number of questions answered) x 4].		
		1	Scoring should always value best
			health as $= 100$, and other optional
			choices to range down to $= 0$.
			Scoring steps then should recognize
			the number of steps from 0 to 100
	45-64	42-61	units.
Subject Symptoms	HJ-04	42-01	units.
(including 4	Double Images:	Double Images:	Example 1) PRQ61a: In the last 7
symptom groups,	45-49	42-46	1 / ~
double images, glare, halo, and starbursts)	Glare: 50-54	42-40 Glare: 47-51	days, how often have you seen starbursts when you are wearing
	Halo: 55-59	Halo: 52-56	your best vision correction (glasses
, ,	Starburst: 60-64	Starburst: 57-61	or contact lenses)?
			I do not wear glasses or contact
			lenses = N/A
			Never $= 100$
	1	1	Rarely $= 75$
			Sometimes = 50

			Often = 25
			Always = 0
	Domain scor	e = (sum of score	Example 2). PRQ60: In the last 7 days, have you seen any starbursts? Yes, but ONLY when NOT wearing glasses or contact lenses = 100/3 Yes, but ONLY when wearing glasses or contact lenses = 200/3 Yes, when wearing AND when not wearing glasses or contact lenses = 0 No, not at all = 100 es of all questions within the domain)/(total
			-
		estions answered	e for each symptom group. Questions with
			ed as not answered and excluded from the
	calculation.	wa wili be treat	ed as not answered and excluded from the
		67	Ves en no secrito a norde d
	12-13	6-7	Yes or no, no scoring needed
	14	8	Mainly vision Mainly other reason Both vision and other reasons No scoring needed
Driving	15-17	9-11	No difficulty = 100 A little difficulty = 75 Moderate difficulty = 50 Extreme difficulty = 25 Never drive during the daytime because of vision, or Never drive at night because of vision or Never drive in these conditions because of vision = 0 Never drive during the daytime for other reasons, or Never drive at night for other reasons, or Never drive in these conditions for other reasons = N/A
	18	12	No difficulty at all =100 A little difficulty = 200/3 Moderate difficulty = 100/3 A lot of difficulty = 0
	Domain score questions ans		es of scores of all questions)/(total number of

	Note: Questions with answers as N/A will be treated as not answered and excluded from the calculation. Questions PRQ12, 13, 14 (or POQ6, 7, 8) are excluded from the domain score calculation.		
	34, 35, 36	28, 29, 30	Yes = 0 No = 100
Vision Clarity	34a, 35a, 36a	28a, 29a, 30a	Very = 0 Somewhat = 25 A little = 50 Not at all = 75
Vision Clarity	Domain score = (sum of scores of all questions within the domain)/(total number of questions answered) Note: When 34 is No, 34A should not be answered. However, in case 34 is No and 34A is answered, ignore 34 result from the domain score calculation and only use 34a result. Apply the same rule when the discrepancy happens to 35 (35A), or 36 (36A), or 28 (28A), or 29 (29A), or 30 (30A).		

 Table 5. PROWL Question Categories and Questions to be Analyzed

Topics - Table Summary with Descriptive Statistics	PROWL-PRQ Questions	PROWL-POQ Questions
Vision Satisfaction	37	34
Vision Clarity	5	5
Satisfaction with LASIK Surgery		71-78

Table 6a. Normalization Scores for PROWL Questions in Table 4

Topics - Table Summary with Descriptive Statistics	PROWL-PRQ Questions	PROWL-POQ Questions	Normalized Score
Vision Satisfaction	37	34	Completely satisfied = 100 Very satisfied = 80 Somewhat satisfied = 60 Somewhat dissatisfied = 40 Very dissatisfied = 20 Completely dissatisfied = 0
Vision Clarity	5	5	Perfectly clear = 100 Pretty clear = $200/3$ Somewhat clear = $100/3$ Not clear at all = 0
Satisfaction with LASIK Surgery		71-78	Scoring of each of these questions should be provided as percentages for each possible response.

Statistical Analysis Plan Version 1.0 / Protocol Number: 884

	Example 1) POQ72:
	Currently, how satisfied or
	dissatisfied are you with
	how long it took to see
	improvement in your vision
	after LASIK surgery?
	Completely satisfied = 100
	Very satisfied = 80
	Somewhat satisfied $= 60$
	Somewhat dissatisfied = 40
	Very dissatisfied = 20
	Completely dissatisfied $= 0$
	Never had any improvement
	in any vision after LASIK
	surgery $= 0$
	Example 2) POQ 73:
	Currently, how satisfied or
	dissatisfied are you with
	how long it took to see
	improvement in your post-
	operative symptoms of
	discomfort after LASIK
	surgery?
	Completely satisfied = 100
	Very satisfied = 80
	Somewhat satisfied = 60
	Somewhat dissatisfied = 40
	Very dissatisfied $= 20$
	Completely dissatisfied $= 0$
	Never had any post-
	operative symptoms of
	discomfort after LASIK
	surgery = 100
	<pre>score = (sum of scores of scores of all questions)/(total</pre>
number	of questions answered)

A data listing by subject of PROWL-PRQ responses and PROWL-POQ responses by study visit also will be presented.

